4.2.3 Expansion Cohort in Solid Tumors and Lymphoma

An additional 24 participants with incurable solid tumors will be treated at the MTD, according to the treatment schedule defined above for each stratum. If the MTDs differ between the two strata, expansion cohorts of six participants each will be enrolled.

Another 24 participants with incurable solid tumors will be treated at single agent nivolumab 240 mg every 2 weeks. Only those histologies that are not known to respond to single agent nivolumab will be excluded (i.e., pancreas, prostate, MSS colorectal cancer, unless results from another clinical trial showing non-response in another tumor type become available in the future).

Participants with HL will be treated at the FDA approved flat dose of 240mg given every 2 weeks.

Participants with an overall response of SD, PR, CR, or unconfirmed PD at the end of the first four cycles of nivolumab will continue treatment for up to a total of 46 cycles of nivolumab (with ipilimumab if receiving dose level 2 or -2) (refer to Section 9.1 for RECIST Criteria and Section 9.3 for the 2017 response evaluation criteria in lymphoma (RECIL) Criteria for evaluating measurable disease in HIV-cHL).

Participants with a confirmed PD will discontinue the study drugs.

4.3 Treatment Plan

4.3.1 Nivolumab

For Dose Levels 1 and -1 in Stratum 1

1 cycle = 14 days

Treatment: A maximum of 46 cycles of nivolumab will be given every 2 weeks.

Dose Level 1: Nivolumab 3mg/kg q 2 wk x 46 doses

Dose Level -1: Nivolumab 1mg/kg q 2 wk x 46 doses

Nivolumab will be given every two weeks (± 2 days) when given as a single agent as per the dose de-escalation table in Section 4.2 and will be modified in cohorts of up to six participants (as outlined in Section 4.2) based upon the number of participants who have a DLT event at each dose level (as defined in Section 4.2) during the first cycle of therapy. Participants may be dosed no less than 12 days from the previous dose of drug.

The dosing calculations should be based on the actual body weight. If the participant's weight on the day of dosing differs by >10% from the weight used to calculate the original dose, the dose must be recalculated. All doses should be rounded to the nearest milligram. There will be no dose modifications allowed.

Nivolumab is to be administered as a 60-minute IV infusion, using a volumetric pump with a 0.2 to 1.2 micron in-line filter at the protocol-specified dose. The drug can be diluted with 0.9% normal saline for delivery, but the total drug concentration of the solution cannot be below 0.35 mg/mL. It is not to be administered as an IV push or bolus injection. At the end of the infusion, flush the line with a sufficient quantity of normal saline.

For the solid tumor expansion cohort, a dose of 240mg of single agent nivolumab will be administered every 2 weeks for 46 doses as described above, as a 60-minute IV infusion.

For the cohort of HL, a dose of 240mg flat dose of single agent nivolumab will be administered every 2 weeks for 46 doses as described above, as a 60-minute IV infusion.

For nivolumab and ipilimumab combination studies see Section 4.3.2.

4.3.2 Nivolumab and ipilimumab

For Dose Levels 2 and -2 in Stratum 1

1 cycle = 14 days

Nivolumab treatment: A maximum of 46 cycles of nivolumab will be given every 2 weeks

Ipilimumab treatment: A maximum of 16 cycles of ipilimumab given every 6 weeks (on day 1 of every third nivolumab cycle (cycles 1, 4, 7, etc.)) for Dose Level 2, and a maximum of eight cycles of ipilimumab given every 12 weeks, (on day 1 of every sixth nivolumab cycle (cycles 1, 7, 13, etc.)) for Dose Level -2.

Dose Level 2:

- Nivolumab 240 mg q 2 wk x 46 doses
- Ipilimumab 1mg/kg q 6 wk x 16 doses (day 1 of nivolumab cycles 1, 4, 7, 10, 13, 16, 19, 22, 25, 28, 31, 34, 37, 40, 43, and 46)

Dose Level -2:

- Nivolumab 1 mg/kg q 2 wk x 46 doses
- Ipilimumab 1mg/kg q 12 wk x 8 doses (day 1 of nivolumab cycles 1, 7, 13, 19, 25, 31, 37, and 43)

Toxicity management for the combined agents follows the same template guidelines and algorithms that are provided in Appendix X for single agent nivolumab.

Follow the same infusion timing guidelines: nivolumab over 60 minutes and ipilimumab over 90 minutes.

When both nivolumab and ipilimumab are to be administered on the same day, separate infusion bags and filters must be used for each infusion. Nivolumab is to be administered first. The nivolumab infusion must be promptly followed by a saline flush to clear the line of nivolumab before starting the ipilimumab infusion.

Nivolumab cycles may be repeated every 14 days (\pm 2 days). Cycles in which nivolumab and ipilimumab are administered, per the dosing schedule for the assigned dose level 2 or -2, no earlier than 12 days after the last cycle of nivolumab.

4.3.3 Stratum 2 treatment

Stratum 2 dosing will begin based on the single agent therapy MTD determined in Stratum 1. Stratum 2 will not be allowed to escalate beyond the MTD for Stratum 1. An expansion cohort will be treated at the MTD for Stratum 1. If the MTDs differ between the two strata, expansion cohorts of six participants each will be enrolled.

4.3.4 Expansion cohorts

For the solid tumor expansion cohort, a dose of 240 mg of single agent nivolumab will be administered every 2 weeks for 46 doses as described above, as a 60-minute IV infusion. Inclusion criteria for CD4 count will be managed as noted in Section 4.1.

1 nivolumab cycle = 14 days

A maximum of 46 cycles of nivolumab will be given every 2 weeks. If the combination is tolerated, ipilimumab will be given according to the treatment instructions for dose level 2 or -2 as above, depending on the MTD for that stratum, in a separate solid tumor expansion cohort.

For the combination solid tumor expansion cohort, the dosing will be 12 intravenous (IV) infusions of nivolumab, 240 mg, on day 1 of each 2-week cycle and ipilimumab on day 1 every 6 weeks with four total ipilumimab cycles, i.e., every third cycle (cycles 1, 4, 7, 10). After completion of the 12th cycle of nivolumab, the nivolumab dose will change to a flat dose of 480 mg, on day 1 of

each 4-week cycle without ipilimumab. Participants with an overall response of SD, PR, CR, or unconfirmed PD at week 8 will continue treatment (Refer to Section 9.1 for RECIST Criteria) for up to 84 weeks. For participants with HIV-cHL, single agent nivolumab will be given as a flat dose of 240 mg every 2 weeks as described in Section 4.3.1.

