The combination therapy MTD will then be studied in a dose expansion cohort (12 participants) limited to only participants with Kaposi sarcoma, lung cancer, and anal cancer; CD4+ count eligibility criteria in the expansion cohort will be determined after reviewing results from Strata 1 and 2. If the MTDs differ between the two strata, expansion cohorts of six participants each will be enrolled. The study treatment consists of 12 IV infusions of nivolumab, 240 mg, on Day 1 of each 2-week cycle and ipilimumab on Day 1 every 6 weeks with four total ipilimumab doses, i.e., every third cycle (cycles 1, 4, 7, 10). After completion of the 12th cycle of nivolumab, the nivolumab dose will change to a flat dose of 480mg, on Day 1 of each 4-week cycle without ipilimumab. Participants with an overall response of SD, PR, CR, or unconfirmed PD at Week 8 will continue treatment (Refer to Section 9.1 for RECIST Criteria) for up to 84 weeks.

A single agent expansion cohort of 24 participants with solid tumors, excluding those histologies not known to respond to single agent nivolumab (i.e., pancreas, prostate, and microsatellite stable [MSS] colorectal cancer) and with CD4 count above 200 will receive single agent nivolumab at 240mg administered every 2 weeks for up to 46

^{**} After evaluating single agent nivolumab dosing, the next dose level will be 2 if dose level 1 is the MTD for single agent nivolumab and dose level -2 if dose level -1 is the single agent MTD. It is also possible to de-escalate from dose level 2 to -2.

doses, or until disease progression, toxicity, study termination, or study withdrawal.

Another single agent cohort of 12 participants with relapsed refractory HIV-associated cHL and with CD4 counts ≥ 100/mm³, will also be treated with single agent nivolumab at a flat dose of 240mg administered every 2 weeks for 46 doses or until disease progression, toxicity, study termination, or study withdrawal (See Section 9.3 for the 2017 response evaluation criteria in lymphoma (RECIL) Criteria for evaluation of measurable disease in HIV-cHL and Section 4.7 and 4.9 for study duration and criteria for removal from study). Participants with an overall response of SD, PR, CR, or unconfirmed PD at Week 8 will continue treatment. Of note, this dose showed no dose-limiting toxicity (DLT) in this trial and is the current FDA approved dosing regimen for non-HIV classical Hodgkin lymphoma.

Duration: Maximum of 92 weeks of treatment

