2.3.9 Dosing revision for nivolumab single agent and combination therapy (April 2019)

In the previous version of this protocol the combination therapy dose was nivolumab 240 mg flat dose q 2 week (IV) with ipilimumab 1 mg/kg q 6 week (IV) for the duration of the study. This dose was found to be tolerable in Stratum 1 Dose Level 2 for participants with a CD4 count above 200 cells/mL. Between May 2017 and February 2018, the FDA updated the label for OPDIVO® to indicate a dosing schedule with only four doses of ipilimumab followed by single agent therapy for advanced RCC and colorectal cancer amd single agent therapy has been updated for many indications to allow 240 mg q 2 week or 480 mg q 4 week, as equal efficacy has been shown for both doses.

This change will be applied to the combination therapy expansion cohort for which tolerability of the original combination therapy has already been established. The new combination therapy will remain the same for four cycles of combination therapy and will then change to single agent therapy with a flat dose of 480 mg q 4 week. This change will bring treatment in line with suggested dosing as well as reducing the burden on study participant by reducing number of visits required.

For single agent therapy in participants with classical Hodgkin's Lymphoma the dose was 3 mg/kg q 2 week. The updated label has been changed for this indication, to a flat dose of nivolumab of either 240 mg q 2 week or 480 mg q 2 week. The protocol dose for the cHL expansion cohort will be updated to 240 mg q 2 week to reflect this change.

Both of these changes will be implemented with version 10.0 of the protocol.

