4.6.4 Precautions

Combination therapy may result in unexpected toxicity especially in novel combinations with other immune modifying agents. A striking example in macaques is presented in Vaccari, *et al.* 2012.

Please note that while unproven, there is a suggestion that autoimmune events, including hepatitis, may occur more frequently at sites of metastases or prior injury.

Caution is advised when considering treatment with high dose IL-2 in participants who have previously been administered ipilimumab, particularly in participants who experienced ipilimumab-related diarrhea/colitis. Colonoscopy or sigmoidoscopy with biopsy may be advisable prior to IL-2 administration once the participant is no longer receiving ipilimumab.

Participants who have received ipilimumab may potentially develop autoimmune disease with subsequent therapy including the appearance of colitis, hypophysitis, or adrenal insufficiency.

4.7 **Duration of Therapy**

In the absence of treatment delays due to AE(s), treatment may continue 92 weeks of nivolumab (with ipilimumab, if receiving dose level 2 or -2) until one of the following criteria applies:

• The development of progression (confirmed PD by RECIST Criteria or PD by the KS evaluation criteria in Section 9.2 or per Section 9.3, utilizing the consensus RECIL (2017). Participants will remain on study treatment until progression is confirmed,

Pregnancy

- All WOCBP should be instructed to contact the investigator immediately if they suspect they might be pregnant (e.g., missed, or late menstrual period) at any time during study participation. Institutional policy and local regulations should determine the frequency of on study pregnancy tests for WOCBP enrolled in the study.
- o The investigator must immediately notify CTEP in the event of a confirmed pregnancy in a study participant.
- Intercurrent illness that prevents further administration of treatment.
- Unacceptable AE(s) which include the following (see also Section 6.0 and specific algorithms in Appendix X):
 - o Any grade 4 events except as noted below.
 - o Grade 3 drug-related autoimmune or inflammatory events including uveitis, pneumonitis, diarrhea, colitis, neurologic AEs, hypersensitivity reaction, or infusion reaction of any duration requires discontinuation except as noted below:
 - o Any other grade 3 non-skin, drug-related AE lasting >7 days including fatigue.

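### Section 4.3.4 still carries a superseded ipilimumab schedule for the combination solid tumor expansion, and the rules for differing stratum MTDs disagree

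*Combined protocol and SAP*

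**What the plan says.** **Regimen.** One paragraph of Section 4.3.4 sets a maximum of 46 two-week nivolumab cycles and then, on condition that combination treatment proves tolerable, adds this instruction: "ipilimumab will be given according to the treatment instructions for dose level 2 or -2 as above, depending on the MTD for that stratum". Section 4.3.2 defines level 2 as 16 ipilimumab doses and level -2 as 8. The next paragraph of 4.3.4, opening with the combination solid tumor expansion by name, orders 12 nivolumab infusions of 240 mg and "ipilimumab on day 1 every 6 weeks with four total ipilumimab cycles", followed by nivolumab 480 mg every 4 weeks without ipilimumab. The synopsis repeats this second regimen. Section 2.3.9, which introduces it with version 10.0, says: "This change will be applied to the combination therapy expansion cohort for which tolerability of the original combination therapy has already been established".

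Section 4.2.3 keeps the older approach. The expansion participants "will be treated at the MTD, according to the treatment schedule defined above for each stratum", and responders or stable participants continue for "up to a total of 46 cycles of nivolumab (with ipilimumab if receiving dose level 2 or -2").

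**Differing MTDs.** The synopsis and Sections 4.1, 4.2.3 and 4.3.3 split the expansion into two cohorts of six. Schema footnote ** and Section 10.1.2 split it 18 and six. Schema footnote * confines it to the Stratum 1 dose in participants with CD4 above 200. On what is known so far, Section 2.3.9 says of level 2: "This dose was found to be tolerable in Stratum 1 Dose Level 2 for participants with a CD4 count above 200 cells/mL". No Stratum 2 combination MTD is reported. The synopsis leaves the CD4 limit open: "CD4+ count eligibility criteria in the expansion cohort will be determined after reviewing results from Strata 1 and 2".

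**Missed doses.** Section 4.5 puts visits after a missed dose back on a 2-week schedule and makes no exception for the 4-week phase.

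**The concern.** Two adjacent paragraphs of the treatment plan address the same cohort and cannot both be followed. A site acting on the leftover paragraph would go on giving ipilimumab in a phase meant to be nivolumab alone. Section 4.4 warns that the combination may increase the frequency and severity of immune-related events, so this bears on safety. It would also place two regimens under one label in the toxicity summaries by dose group planned in Section 10.1.2.

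The second part concerns what happens if Stratum 2 does not tolerate level 2. The governing regimen is a fixed one, built on 240 mg nivolumab and ipilimumab every 6 weeks. The leftover sentence is the only place in 4.3.4 that provides for level -2. Deleting it without settling one rule for differing MTDs would leave that case without a regimen.

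**Working it through.** **1. The plan's own dose counts.** Level 2 gives ipilimumab at cycles 1, 4, ..., 46: (46 - 1)/3 + 1 = 16. Level -2 gives it at cycles 1, 7, ..., 43: (43 - 1)/6 + 1 = 8. Both match Section 4.3.2. The governing regimen uses cycles 1, 4, 7 and 10, which is 4 doses.

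**2. Level 2, to week 24 (cycles 1-12).** Both texts give 4 ipilimumab doses and 12 x 240 mg = 2,880 mg nivolumab. There is no difference.

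**3. Level 2, week 24 to week 92** (week 8 plus up to 84 weeks).
- Ipilimumab: 16 - 4 = 12 doses under the leftover text, 0 under the governing one.
- Nivolumab, leftover: (46 - 12) x 240 mg = 34 x 240 = 8,160 mg.
- Nivolumab, governing: (92 - 24)/4 = 17 doses; 17 x 480 = 8,160 mg.
- Infusion visits: 34 versus 17.

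The drug difference is therefore ipilimumab alone, provided treatment runs to week 92. Section 8.6 lists this cohort's visits only to cycle 23. That is 11 four-week doses, 24 + 11 x 4 = 68 weeks and 11 x 480 = 5,280 mg, against 8,160 mg for 46 two-week cycles. If both schedules are compared only to week 68, the leftover text adds ipilimumab at cycles 13, 16, 19, 22, 25, 28, 31 and 34, so 8 versus 0.

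**4. If Stratum 2's combination MTD were level -2.** By week 24 the fixed regimen gives 4 ipilimumab doses against 2 (cycles 1 and 7). Nivolumab per infusion is 240 mg against 1 mg/kg. At assumed weights of 50, 70 and 100 kg the ratios are 240/50 = 4.8, 240/70 = 3.4 and 240/100 = 2.4. Over 92 weeks the fixed regimen gives less ipilimumab in total, 4 against 8. The excess in ipilimumab is early only.

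**5. The differing-MTD rules side by side.**

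| Rule | Where | CD4 100-200 participants |
|---|---|---|
| Six in each stratum | Synopsis, 4.1, 4.2.3, 4.3.3 | 6 of 12 |
| 18 and six | Schema footnote **, 10.1.2 | 6 of 24 |
| Stratum 1 dose, CD4 above 200 only | Schema footnote * | none |

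The maximum of 96 in Section 10.2 is 18 + 18 + 24 + 24 + 12, so it assumes a combination expansion of 24. With 12 the sum is 84. Whether the undivided cohort is 12 or 24 is a separate discrepancy.

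**The case against.** The strongest reply is that no site would follow the leftover sentence. The governing paragraph comes straight after it, the synopsis and 2.3.9 agree with it, and this cohort has its own visit section (8.6, to cycle 23). Its schedule in Appendix I ends at cycle 22, and its serial HIV blood draws fall at cycles 1, 4, 7 and 10, exactly the four ipilimumab cycles. This stands as far as likelihood goes: a reader might infer that continued ipilimumab dosing is to be expected, and the documents do not support that. It does not remove the contradiction, because 4.3.4 states no precedence and 4.2.3 repeats the old text.

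Other replies also have force:

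- **Section 4.7.** A reader might see a third contradiction in "treatment may continue 92 weeks of nivolumab (with ipilimumab, if receiving dose level 2 or -2"). It is a duration rule, conditional on receiving level 2 or -2, and its 92 weeks fit the governing regimen. Clarifying it is optional.
- **Section 3.3.** A reader might infer that its fallback clause opens the combination expansion to any CD4 count. That clause carries the single agent cohort's histology exclusions, and 3.1.10 reserves the CD4 limit for later. Clarifying it is optional too.
- **Schema footnotes.** The figure is not shown, so what each footnote marks is unknown. The clash between six each and 18 and six survives without it, because both are printed in body text.
- **Dose in 4.3.3.** It can be read as a default at the Stratum 1 MTD with an exception if the MTDs differ. That is fair, but the exception still lacks a level -2 regimen.
- **Section 4.5.** Doubling the visit rate in the 480 mg phase needs a literal reading of text that was not updated. It is minor.

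**Conclusion.** The regimen conflict in 4.3.4, echoed in 4.2.3, is real, and the four-dose regimen governs. At an MTD of level 2 its size is 12 versus 0 ipilimumab doses after week 24, assuming treatment to week 92. Nivolumab totals are equal on that same assumption only. The safety consequence is possible rather than probable, given the cohort's own schedules.

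The conflict among the differing-MTD rules is also real, but it takes effect only if Stratum 2's combination MTD falls below level 2. A reader might conclude that CD4 100-200 participants will be dosed above their MTD. The documents do not support that. It would need a Stratum 2 MTD of -2, a decision to admit CD4 100-200, and use of the fixed regimen despite the texts in 4.1, 4.2.3 and 4.3.4 that dose by stratum MTD. The body weights used to size that case are assumptions.

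Nor do the documents require footnote * to prevail. It would remove the CD4 100-200 group that the other rules plan for, which is a design choice for the sponsor.

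**What to change.** 1. In 4.3.4 and 4.2.3, delete the 46-cycle and level 2/-2 wording as it applies to the combination expansion and state only the four-dose regimen. Keep 46 cycles for the single agent solid tumor and cHL cohorts.
2. In the same amendment, have the sponsor choose one rule for differing MTDs and state it identically in the synopsis, schema, 4.1, 4.2.3, 4.3.3 and 10.1.2. Specify that CD4 100-200 participants do not receive the fixed four-dose regimen unless Stratum 2 clears level 2. Footnote * is one option. If a CD4 100-200 group is kept at level -2, write out its regimen.
3. Minor: in 4.5, have visits after a missed dose in the 480 mg phase resume every 4 weeks.
4. Optional: add this cohort's four-dose limit to 4.7, and separate the CD4 and histology rules in 3.3.

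Items 1, 3 and 4 are wording changes with no added participants or procedures. Item 2 is a design decision. Choosing footnote * would mean no expansion data in CD4 100-200 if Stratum 2 does not clear level 2. The 12-versus-24 cohort size needs its own correction.

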4.3.5 Study procedures by visit and treatment cycle

Note that results of all safety laboratory test (that is, all chemistry and all hematology results) must be obtained and reviewed before ipilimumab administration, as applicable. All laboratory results must be within the established range before ipilimumab is administered. All laboratory samples for the first four cycles of nivolumab must be collected within a window of up to 3 days before administration of nivolumab and/or ipilimumab. Laboratory evaluations using a local laboratory must be performed and the result examined by the investigator before administration of each dose of nivolumab and/or ipilimumab.

4.4 Definition of DLT

Nivolumab has the potential to be synergistic with ipilimumab and augment the rate and duration of clinical responses. It also, however, has the potential to augment the frequency and severity of previously characterized ipilimumab-related immune-related adverse events (irAE), as well as to generate new study drug-related irAEs or toxicities. It will be important to differentiate between irAEs expected from ipilimumab toxicity as opposed to an increase in frequency or a worsening of severity of irAEs as an indicator of unacceptable toxicity related to the combination.

The MTD to define the optimal dose. The MTD itself is determined by DLT, i.e., toxicity/severity that limits the possibility to treat a participant at the planned dose. DLT is traditionally defined as any grade 3-4 non-hematological or grade 4 hematological toxicity at least possibly related to the treatment, occurring during the first cycle of treatment. DLTs will be defined by drug-related AEs that meet the criteria below as evaluated by NCI Common Terminology Criteria for AEs version 5 (CTCAE v5.0), unless clearly unrelated to study drugs (e.g., disease progression) defined based on DLTs that occur during the first 6 weeks for single agent nivolumab (Dose Levels 1 and -1) and 6 weeks for the nivolumab and ipilimumab combination (Dose Levels 2 and -2).

Note: DLT and other toxicities are discussed among the Study Chair, Co-Chairs, the Phase I Committee Chair, the AMC Medical Monitor, and the AMC Biostatistician. The discussions are the basis for the decisions regarding dose de-escalation according to the rules of the protocol and opening of Stratum 2 to enrollment.

- Permanently stopping protocol treatment during the DLT period (defined as 6 weeks from the first dose) for either arm is considered a DLT.
- Any drug-related death is a DLT.
- Grade 3 or 4 events requiring permanent discontinuation of nivolumab or ipilimumab, including those that will require long term, high dose corticosteroids.

Management and dose modifications associated with the above AEs are outlined in Section 5.0 and Appendix X.

